2.3.1 Differential Gene Expression analysis

Firstly, we will conduct outlier analysis using data visualization methods such as Principal Component Analysis, Boxplots, Hierarchical Clustering and IQR/Median plots. After testing for potential outliers, non-specific filtering will be conducted on our dataset to remove any very lowly expressed genes. Differential expression testing will be conducted in R version 4.1.2 using the Bioconductor package DESeq2(3). The data will be normalized with the DESeq2 mean of ratios method and baseline characteristics will be controlled for using the function design(model). We will first compare, for each drug arm, differentially expressed genes at pre-treatment versus post-treatment to understand the biological pathways driving drug response. We will modify our analysis as results evolve to test for differences in gene expression and identify transcriptomic gene signatures for genes and/or pathways driving differences between responders and non-responders for each drug. We will then compare gene expression between each treatment and SoC. We will also build smaller models comparing Differentially Expressed Gene (DEG) analysis between drug groups.

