1.2.1 Datasets

The datasets generated from the above sampling protocol of the ACCORD trial include transcriptomics, proteomics, viral load, serology, pharmacokinetic drug concentration and clinical laboratory datasets. Further information about the generation and processing of each dataset is outlined below:

1.2.1.1 Transcriptomic dataset (RNA Sequencing)

Sequencing was performed on patient blood samples taken on days 1 (at baseline prior to treatment), day 5 and day 10 of admission to hospital. A total of 286 samples were sequenced using an Illumina NovaSeq 600 platform. Total RNA was prepared from blood and depleted of highly abundant transcripts for alpha and beta haemoglobin and ribosomal RNA. No more than 50 samples per 'lane' were multiplexed to maximise sequence read depth to ensure a minimum sample read depth of 100 to 150 M. Quality control (QC) of raw read data was performed using FastQC version 0.11.9 and compiled and visualised using MultiQC version 1.12. Samples with <20 million total reads and less than 50% of the total read count were excluded from further analysis. After MultiQC analysis, fourteen sample were removed that failed quality control, leaving 272 high-quality samples available in the transcriptomic dataset for downstream analysis.

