2.2 Comparison and confounding of baseline clinical characteristics

Baseline clinical characteristics, including age, sex, ethnicity, significant comorbidities, laboratory results and clinical observations will be recorded, assessed and compared between patients in different treatment arms using R (v 4.1.2). Patient statistics tables will be calculated to test for any significant confounding variables between blinded groups. Principal component analysis of normalised expression values will be correlated with axes of variation e.g. ethnicity, to identify clusters affecting gene expression.

Differential gene expression analysis will control for baseline factors that may skew analysis by updating the statistic model design in DESeq2. Differential splicing analysis will be subject to weighting by multinomial covariate-balanced propensity scores to control for baseline confounding factors, as implemented by the R package Weightlt version 0.12.0, using the "just-identified" approach. Proteomics models will incorporate weighted baseline clinical data to avoid bias.

2.3 Transcriptomic analysis

The focus of this study will be the analysis of the transcriptomics dataset comprising patient data taken at three time points for three novel drugs and the SoC trial arm. The RNA-Sequencing samples have been generated and the raw FASTQC data have been downloaded from the ACCORD clinical trials platform. These data have been subject to quality control as previously described in the methods section. To avoid any unintentional bias, the groups will be blinded so that the bioinformatician will not know which patient group or SoC arm is which. The novel drug and SoC arms will be given a random identifier such as A, B, C or D for the duration of this analysis.

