2.3.4 Differential splicing analysis

High quality data passing multiQC analysis will be retained for downstream differential splicing expression analysis. STAR version 2.7.1 software will be used to generate an index file mapped to the Human Genome Reference GRCh38 primary assembly and the GENCODE v34 annotation and generated using STAR's genome generate function with the argument - sjdbOverhang 149 and all other settings as default. Individual FASTQ files will be subsequently aligned to GRCh38 using STAR. Resultant unsorted BAM files will be sorted using Samtools version 1.16. Splicing junction files will be generated using RegTools version 0.5.2, and resultant files will be inputted into LeafCutter version 0.2.9 software for differential splicing analysis. Leafcutter only supports comparison of two groups and therefore differential splicing will be compared for each treatment group pre- and post-treatment and then between treatment and SoC. We will implement MAGIQ version 2.3 software for multigroup differential splicing analysis to compare each drug arm.

In summary, this transcriptomic analysis plan will interrogate our transcriptomic dataset on a pathway level as well as on an individual gene basis and enable a full characterisation of the molecular mechanisms and drivers of severe COVID-19 disease response to novel drugs.

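### The within-arm pre/post expression and splicing contrasts use repeated samples from the same patients, but the only controls named are baseline covariates and propensity weights, with no patient term

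*Protocol*

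**What the plan says.** - **Sampling.** Section 1.2.1.1: "Sequencing was performed on patient blood samples taken on days 1 (at baseline prior to treatment), day 5 and day 10 of admission to hospital". Section 2.3 describes the data set as "patient data taken at three time points for three novel drugs and the SoC trial arm".
- **Expression contrast.** Section 2.3.1: "We will first compare, for each drug arm, differentially expressed genes at pre-treatment versus post-treatment". Responder, drug versus SoC and drug versus drug comparisons follow.
- **Expression model.** Just before that list of contrasts, section 2.3.1 states that "baseline characteristics will be controlled for using the function design(model". Section 2.2 likewise refers only to baseline factors.
- **Splicing contrast.** Section 2.3.4, for the two-group LeafCutter method: "differential splicing will be compared for each treatment group pre- and post-treatment and then between treatment and SoC".
- **Splicing control.** Section 2.2: "Differential splicing analysis will be subject to weighting by multinomial covariate-balanced propensity scores to control for baseline confounding factors".

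Neither these sections nor the rest of the protocol names a patient term, a paired test, a random effect or a within-patient correlation for these contrasts.

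**The concern.** A pre/post contrast within one arm compares the same people on different days. Its precision depends on removing stable differences between patients, and the pairing does that. Age, sex, ethnicity, comorbidity and baseline laboratory values do not change between a patient's own two samples. As covariates they remove only the part of the between-patient variation that they explain. Weights that balance arms do not represent pairing at all.

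This goes beyond an unstated detail. Time-constant baseline covariates are collinear with a fixed patient term, so the DESeq2 design as described cannot simply take on a patient factor as well; for this contrast one must replace the other. The plan names the one that leaves the patient variation in the error.

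The gene lists from these contrasts go into the pathway analysis of section 2.3.3, which is meant to point to mechanisms of action. Section 2.6 itself says that the data are few. Within-patient changes missed at this first step are lost to the later ones.

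**Working it through.** The protocol gives no power, alpha or effect size for these tests, so there is no stated figure to reproduce. Its sample count is consistent: 286 sequenced - 14 failing QC = 272.

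**Assumptions (not in the documents).** Equal arms and complete series: 272 / (3 days x 4 arms) = 22.7, taken as n = 23 pairs per arm. Two-sided alpha is 0.05 per gene. Rho is the within-patient correlation left after the baseline covariates, varied from 0.2 to 0.7.

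**Standard error.** With per-sample variance sigma^2:
- SE reported by an unpaired test: sigma x sqrt(2/n) = sqrt(2/23) = 0.295 SD.
- True SE of the paired difference: sigma x sqrt(2(1-rho)/n). At rho 0.5 it is sqrt(1/23) = 0.209 SD.
- Ratio: 1/sqrt(1-rho), or 1.12 at rho 0.2, 1.20 at 0.3, 1.41 at 0.5 and 1.83 at 0.7.

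**True size of the nominal 5% unpaired test** (normal approximation), 2 x [1 - Phi(1.96/sqrt(1-rho))]: 2.8%, 1.9%, 0.6% and 0.03% for the same four values of rho.

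**Power for a 0.5 SD change** (20,000 simulated bivariate-normal data sets, two-sample t versus paired t, 23 complete pairs):

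| rho | unpaired | paired |
|---|---|---|
| 0.2 | 37% | 44% |
| 0.3 | 36% | 49% |
| 0.5 | 34% | 63% |
| 0.7 | 31% | 84% |

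At p < 0.001, closer to genome-wide use, a 0.8 SD change at rho 0.5 gives 16% versus 53%.

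**Do the baseline covariates rescue the test?** A second simulation (4,000 data sets, n = 23) put two baseline covariates in the unpaired model. At rho 0.5 the mean SE was 0.289 unpaired and 0.205 paired. For a change of (1.960 + 0.842) x 0.209 = 0.584 SD, power was 49% versus 76%, and the size of the unpaired test was 0.7%. What matters is the correlation that remains after the covariates.

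**Incomplete series.** With 167 patients randomised in the platform study, three samples each would make 501, against 286 sequenced. Many patients may therefore lack a later sample. The SE ratio at rho 0.5 then changes:
- 23 pre and 13 post, all 13 paired: unpaired variance 1/23 + 1/13 = 0.1204; true variance 0.1204 - 2 x 0.5 x 13/(23 x 13) = 0.0769; ratio sqrt(0.1204/0.0769) = 1.25.
- 13 of 23 patients with both Day 5 and Day 10, pooled as post: 1.19.
- All 167 with Day 1 and 60 with both later days (167 + 120 = 287, close to 286), pooled: 1.07.
- 35 pre and 5 patients with two later samples each, pooled: unpaired variance 1/35 + 1/10 = 0.1286; true variance 0.1286 + 0.5 x 5 x (2/10^2 - 4/(35 x 10)) = 0.1500; ratio 0.93, slightly too narrow.

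In power terms, 23 pre and 15 post samples at rho 0.5 give 27% for the unpaired test on all samples and about 43% for complete pairs. At rho 0.2 with only 10 post samples, complete pairs do worse than the unpaired test (20% versus 23%).

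**The case against.** The strongest reply is that the protocol never says the tests are unpaired. The sentence on baseline characteristics is a general one about DESeq2, placed before the whole list of contrasts, and the design formula for each contrast could be set in a statistical analysis plan. This stands in part: a reader might infer that pairing has been ruled out, and the text does not say so. But the protocol does state what goes into the model, in a section that fixes software versions and even an alignment argument, and the stated terms cannot sit beside a fixed patient term.

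Second, a reader might infer that the arm propensity weights will be applied to the pre/post splicing test. Section 2.2 attaches them to differential splicing in general, and multinomial weights fit a comparison of several arms. No text assigns them to the within-arm comparison. What stands is that their scope is left open.

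Third, it is too strong to say that baseline adjustment does nothing here. That holds for complete pairs. If later samples come from a selected subset, the pre and post sets differ at baseline and adjustment does some work in an unpaired model.

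Fourth, rho, the number of pairs, the effect size and alpha are all assumed, and the main figures come from t-tests, not from DESeq2 with shared dispersion or from LeafCutter. This is correct, and the results above have to be read as a range.

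**Conclusion.** The point holds in a limited form. As written, the plan names no means of using the pairing in its first expression and splicing contrasts, and the baseline terms it does name leave unexplained between-patient variation in the error.

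If most patients have both samples and rho is positive, the tests are conservative. With 23 complete pairs the SE is too wide by a factor of 1.12 at rho 0.2 and 1.41 at rho 0.5, and power for a 0.5 SD change falls from 44% to 37% and from 63% to 34%. Incomplete follow-up weakens this: the factor was 1.07 to 1.25 in three of the incomplete splits tried at rho 0.5, and 0.93 in one sparse split with Days 5 and 10 pooled.

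A reader might take miscalibrated p-values to mean inflated false discoveries. The figures do not support that for the usual case: the test rejects too rarely under the null, so the harm is lost sensitivity. Whether a pre/post change can be credited to the drug is a separate question.

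**What to change.** 1. **Section 2.3.1.** For pre/post contrasts, use a patient blocking term in DESeq2 (~ patient + day) in place of the time-constant baseline covariates, which the patient term absorbs. Keep baseline adjustment for between-arm contrasts.
2. **Section 2.3.4.** Enter patient as a covariate in the pre/post LeafCutter comparison.
3. **Section 2.2.** State that the arm propensity weights apply to between-arm comparisons only.
4. **Incomplete series.** Report how many patients per arm have both samples. If many have only one, use a model with within-patient correlation, for example limma with a patient block, and retain the baseline covariates there because the later samples may be a selected subset.

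The cost is a few sentences and a changed design formula, with no new data. The fixed patient term uses degrees of freedom and drops patients with a single sample. The correlation-based option avoids that loss but replaces DESeq2 for this contrast; at present limma is named in section 2.3.3 only for pathway scores.

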NIHR150393: Exploring and grouping COVID-19 pharmaceutical interventions to determine mechanisms of action and endotypes of response

This project is funded by the NIHR Efficacy and Mechanism Evaluation (EME) Programme (NIHR150393). The views expressed in this protocol are those of the author(s) and not necessarily those of the NIHR, NHS England or the Department of Health and Social Care

1 Research design

This research project is designed to identify the biological mechanisms through which novel COVID-19 drugs provide therapeutic benefit using data obtained from the ACCORD clinical trial(1). We will compare three novel therapeutics (Bemcentinib, Tozorakimab (previously known as MEDI3506) and Zilucoplan) to the Standard of Care (SoC) for severe COVID-19 patients using multiple data types (transcriptomics, proteomics, viral load, and pharmacokinetic drug levels). Each COVID-19 drug will be compared to the SoC of care individually before comparing the identified biological mechanisms comparatively to compare the mechanisms and conditions being modulated favourably by these drugs. Additionally, we will explore biological mechanisms and differences and relationships to effect size of clinical response as measured by time to improvement or discharge. This will better help us understand how the novel drugs work and how to select efficient treatments for a particular patient

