Missing data will be minimised, with outcomes collected after premature withdrawal of treatment. The primary clinical estimate will be analysed using a treatment policy strategy. If an OSS is missing on a particular study day, the unscheduled visits will be considered to see whether there was an unscheduled visit on that day. If so, the score from the unscheduled visit will be used. For the purposes of the primary analysis patients who died or were transferred will not be censored at day of death/transfer, time to clinical response will instead be censored as 29 days. Patients are considered to be in the study until Day 29 but a score of 8 will be imputed for the OSS for those who died from their date of death and for all subsequent visits. Moreover, if a patient withdraws and then dies and we have a record of their death then a score of 8 will be imputed from their date of death onwards for all analyses. For those who transferred, additional data post transfer has been collected and will be used. If a patient is discharged, has no Day 29 value but has a day 60 value they will be considered Alive for the mortality analysis and Last observation carried forward (LOCF) will be used to impute Day 29. If a patient has discharged and no additional data are available, then they are assumed alive at Day 29 and LOCF will be used to impute Day 29 value. If the OSS is missing on the date of discharge, this will be imputed to 2 (most conservative value possible for discharged patients). If the OSS is \geq 3 on the date of discharge, then the score will be imputed to 2. If a patient is subsequently readmitted and has ordinal scale data, then this data will be used. However, if data has not been entered upon readmission, then the patient will be considered a non-responder for the primary endpoint. Once they have been discharged then if OSS is missing it will be imputed as 2 for subsequent days. Reported ethnicity will be compared with ancestral ethnicity inferred using genetics data (Peddy software) and mapping of genotypes to gnomAD v2.1.1 data. Inferred (genetic ancestry) will be preferred over reported ancestry where discrepancies occur. Sex will be calculated counting genotypes on the X chromosome and be used preferentially where gender may not match biological sex.

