2.4 Proteomics Analysis

Following quality control and quantitation of the 27 proteins (undertaken at the Medicines Evaluation Unit as part of the ACCORD trial) we will compare differences between the drugs and SoC arms. The dataset will be visualised using PCA plots with phenotype information overlaid to identify any unknown batches. If detected, batches will be corrected before or accounted for in the statistical modelling. Statistical analysis will be conducted to identify statistical differences between the different groups within this study (Each therapeutic compared to SoC and responders vs non-responders within each therapeutic arm). Shapiro wilk tests will be used but more likely we will use Mann-Witney U Tests between these groups. Following this we will also perform multiple testing corrections to the resulting p values.

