functional relationships we wish to extract via the modelling exercise have similarities to what is acquirable from prior knowledge of other archived data. For example, Bepler & Berger (2021) and Rives et al. (2021), show how models trained on very large protein sequence data capture evolutionary and structural constraints of biology and can be used in subsequent benchmark downstream tasks such as predicting homologous relationships and secondary structures, outperforming models that are trained on the available small datasets alone(10,11). Here, we expect to build on these developments and use existing multi-omics data archived in public repositories to derive usable prior knowledge in models which could help alleviate the issues arising from the small amounts of data we have. Additionally, we will use leave-one-out cross validation, whereby models are trained repeatedly, leaving only a single datum out, and quantifying any inference we draw as averages over the left-out data. This way, statistically meaningful confidence can be derived on any inference we make -- the best one could do when in a limited data setting

References:

- 1. Wilkinson T. ACCORD: A Multicentre, Seamless, Phase 2 Adaptive Randomisation Platform Study to Assess the Efficacy and Safety of Multiple Candidate Agents for the Treatment of COVID-19 in Hospitalised Patients: A structured summary of a study protocol for a randomised. (2020). *Trials*. 21(1). doi:10.1186/s13063-020-04584-9
- 2. Ainsworth M. Performance characteristics of five immunoassays for SARS-CoV-2: a head-to-head benchmark comparison. (2020). *Lancet Infect Dis.* 20(12):1390–400. doi:10.1016/S1473-3099(20)30634-4
- 3. Love MI. Moderated estimation of fold change and dispersion for RNA-seq data with DESeq2. (2014). *Genome Biol.* 15(12):550. doi:10.1186/s13059-014-0550-8
- 4. Langfelder P. WGCNA: An R package for weighted correlation network analysis. (2008). *BMC Bioinformatics*. 9(1):559. doi:10.1186/1471-2105-9-559
- 5. Shannon P. Cytoscape: A software Environment for integrated models of biomolecular interaction networks. (2003). *Genome Res.* 13(11):2498–504. doi:10.1101/gr.1239303
- 6. Hänzelmann S. GSVA: Gene set variation analysis for microarray and RNA-Seq data. (2013). *BMC Bioinformatics*. 14(1):1–15. doi:10.1186/1471-2105-14-7/FIGURES/7

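### Section 2.3.1 commits to changing the responder-signature analysis in the light of results, with no lock point, so nominal p-values or false-discovery rates for those signatures are not guaranteed

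*Protocol*

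**What the plan says.** Protocol section 2.3.1 sets an order of work. It begins: "We will first compare, for each drug arm, differentially expressed genes at pre-treatment versus post-treatment". The next step is the one at issue: "We will modify our analysis as results evolve to test for differences in gene expression". The same sentence gives the aim, which is to find signatures for "genes and/or pathways driving differences between responders and non-responders for each drug". Comparison of each treatment with standard of care comes after that.

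Other sections bear on how much can change:

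- Section 2.2, on covariates: "Differential gene expression analysis will control for baseline factors that may skew analysis by updating the statistic model design in DESeq2".
- Section 1, on response: the interest is in "effect size of clinical response as measured by time to improvement or discharge". No cut is given that makes a patient a responder for the signature analysis.
- Section 2.1 labels some patients non-responders, but only in one situation: "if data has not been entered upon readmission, then the patient will be considered a non-responder for the primary endpoint".
- Section 1.2.1.1 has RNA sampled on days 1, 5 and 10, so there are two post-treatment days to choose from.

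Three safeguards are stated. Section 2.3 masks the arm labels from the bioinformatician. Section 2.4 says, for the 27 proteins: "Following this we will also perform multiple testing corrections to the resulting p values". Section 2.6.5 says, for the machine-learning work: "we will use leave-one-out cross validation".

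**The concern.** A nominal p-value or false-discovery rate has its stated meaning when the test was chosen without sight of the data it is applied to. Section 2.3.1 commits to the reverse order for the responder analysis: results are seen, the analysis is modified, and the modified analysis is run on the same patients. Adjustment across genes deals with the number of genes in one contrast. It does not deal with how many versions of the contrast were tried before one was reported.

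The stake is how the responder signatures can be read. Section 1 hopes that the work will help match treatments to individual patients. A reader of the eventual report could not tell a signature from a contrast fixed in advance from one that emerged after several changes, and both would carry the same kind of p-value.

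**Working it through.** **Is there a figure to reproduce?** No. The protocol gives no alpha, false-discovery level, power or sample size for the responder signatures. Its related counts agree: 286 − 14 = 272 sequenced samples kept, and 60 + 55 = 115 in the additional Bemcentinib study.

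**Do the stated safeguards reach this contrast?**

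- *Arm masking (2.3).* It hides which arm is which. Responder status is not said to be masked, and a within-arm responder contrast can be altered without knowing the drug.
- *Leave-one-out validation (2.6.5).* It is stated for the machine-learning models only and uses the same patients. It cannot undo choices already made on the full data.
- *Multiplicity correction (2.4).* It is named for the protein comparisons. A similar correction across genes would work within one version, not across versions.
- *Additional Bemcentinib study (1.1).* It is not assigned as a hold-out or validation set, and it covers one drug.

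**Illustration 1: independent versions.** Assume 5% per version, no true effect, and the best of k versions kept. The chance of at least one false finding is 1 − 0.95^k:

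| k | 1 − 0.95^k |
|---|---|
| 1 | 5.0% |
| 3 | 1 − 0.8574 = 14.3% |
| 5 | 1 − 0.7738 = 22.6% |
| 10 | 1 − 0.5987 = 40.1% |

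**Illustration 2: overlapping versions on the same patients.** Versions of one contrast share patients and are positively correlated, so illustration 1 overstates the effect. A simulation with no true effects shows how much inflation remains.

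- Arm size, an assumption: 272 / 3 = 90.7 patients if each gave three samples, and 90.7 / 4 = 22.7 per arm if the four arms were equal. Sizes of 15, 23 and 30 were run.
- 2,000 correlated genes, within-patient correlation of 0.5 between days, response unrelated to expression, a linear model per gene, Benjamini-Hochberg at 5% within each version, 500 runs per size.
- One locked version: day 5, median split, unadjusted.
- Four versions: day 5, day 10, change to day 5, change to day 10.
- Twenty-four versions: those 4 × 3 responder cuts × with or without one covariate.

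Chance of at least one falsely declared gene, per drug:

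| Patients per arm | One locked | Best of 4 | Best of 24 |
|---|---|---|---|
| 15 | 5.2% | 18.0% | 58.6% |
| 23 | 4.8% | 18.2% | 55.2% |
| 30 | 4.0% | 15.8% | 51.4% |

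The Monte Carlo standard error at 23 per arm is √(0.048 × 0.952 / 500) = 1.0 point for the locked version and √(0.552 × 0.448 / 500) = 2.2 points for the best of 24. The independent formula gives 18.5% for k = 4 and 70.8% for k = 24. Correlation therefore lowers the inflation but does not remove it, and the locked contrast stays near 5%.

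**The case against.** The strongest objection is that no stated error rate is broken. The protocol promises no alpha or false-discovery level for differential expression, its title speaks of exploring, and section 1 introduces the response work as exploration. This stands. A reader might infer that a confirmatory analysis is being compromised, but the document promises no confirmatory responder result.

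Second, responder definition, sampling day, covariates and false-discovery level are items that a protocol often leaves to a statistical analysis plan. This also stands: their absence is not the point. The point is the positive commitment in 2.3.1. An analysis plan that locked the contrast would contradict that sentence, so leaving it in place is not neutral.

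Third, the sentence may mean only that the model moves from the pre/post comparison to a responder comparison. Those are different contrasts, and seeing an arm's average change does not in itself pick out a favourable responder difference. That reading is possible. A reader might go the other way and infer that the day, covariates or responder cut will be chosen by whatever looks interesting, and the text does not say that either. On both readings, however, the sentence sets no limit on the change and no rule for which version is reported.

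Fourth, the section 2.4 protein comparisons of responders with non-responders use a separate platform with multiplicity correction, and the co-expression modules in 2.3.2 are built unsupervised. These are useful supporting evidence. They come from the same trial's patients and do not replace a fixed contrast.

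Finally, it would be tempting to equate responder signatures with the endotypes of the title. The protocol does not define one as the other, and the point does not depend on it.

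**Conclusion.** The concern holds in a limited form. Section 2.3.1 commits to results-driven modification of the responder analysis on the same patients with no lock point, and no stated safeguard covers the choice among versions. Nominal p-values or false-discovery rates attached to the resulting signatures are therefore not guaranteed.

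The size is unknown. The 14% and 40% figures, and the simulated 16% to 59%, rest on an assumed 5% level, assumed arm sizes, no true effects and an invented set of versions. They show that the inflation can be material. They are not estimates of this project's false-positive rate, and a reader should not take them as such. For largely exploratory work, the remedy is a clear separation of fixed from results-driven analyses rather than a ban on the latter.

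**What to change.** Replace the sentence in section 2.3.1 with text to this effect:

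1. Before responder status is linked to the expression data, one main responder contrast per drug is locked: responder definition, sampling day, covariates and false-discovery level. It is reported as the main responder result for that drug.
2. Every later version is reported, including those that found nothing, and is labelled post hoc or exploratory.
3. No false-discovery rate is claimed for a later version unless the selection was written as an algorithm and the whole of it was rerun under permuted responder labels.

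Locking before arm unmasking would not be enough, because only arm labels are masked and responder results could already have been seen. The permutation route in item 3 is open only for selection that can be rerun mechanically. Choices made by judgement cannot be repeated under permuted labels.

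The lock costs about a page of text. The permutation route costs more, since the selection must be coded first, but it is optional. Exploration stays open, and the small downside is that later signatures carry a weaker label.
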